To test this hypothesis, we propose the following Specific Aims:

- 1) To determine whether vitamin D₃ (4,000 IU per day for at least one year) will result in a significant improvement of the pathology status at repeat biopsy in subjects taking vitamin D₃, compared to subjects taking placebo. This hypothesis will be tested through a randomized clinical trial, which will enroll 136 subjects (68 participants per arm), diagnosed with early-stage prostate cancer (Gleason score ≤6, PSA ≤10, clinical stage T1C or T2a). The pathology status will be measured by the change in Gleason score and the number of positive cores in prostate needle biopsy specimens between baseline and the end of the study. Pre- and post-study biopsies will be performed as part of the standard medical care for diagnosis and active surveillance.
- 2) To determine whether vitamin D₃ supplementation, compared to placebo, will result in a significant decrease in the number of subjects who will undergo additional treatment (hormone therapy, prostatectomy, or radiation therapy), following the outcome of repeat biopsy.
- 3) To analyze changes in the serum levels of cholecalciferol, 25(OH)D, 1,25(OH)₂D, and prostate-specific antigen (PSA) at baseline and at the end of the study, and to estimate the associations between changes in these measures and pathology outcomes (Gleason score and number of positive cores).
- 4) To compare the expression of molecular biomarkers, which are prognostically relevant to prostate cancer progression, in pre- and post-treatment biopsy tissue specimens. Paraffinembedded sections will be processed to assess by immunohistochemical techniques the

- expression of the following biomarkers: vitamin D receptor (VDR), 25-Hydroxyvitamin D $_3$ 1-alpha-hydroxylase (CYP27B1), p21, tumor growth factor β (TGF β), cyclooxygenase 2 (COX-2), and NF κ B. All of these protein products impact growth control and chronic inflammation in prostate cancer progression and are specifically affected by vitamin D status.
- 5) To determine psychological and physiological stress response for patients involved in prostate cancer screening and treatment options by administering a survey about the patients' prostate biopsy decision making experience and obtaining measurements (Allostatic load parameters) of stress response at the beginning and end of the study visits.

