Expression of VDR (C-20 rabbit polyclonal, Santa Cruz biotechnology), p21 (CP74 monoclonal antibody, SIGMA), TGF β (HPA027923 rabbit polyclonal, SIGMA), COX-2 (H-62, rabbit polyclonal, Santa Cruz biotechnology) will be measured by immunohistochemistry on de-identified sections of pre- and post-study biopsy specimens of enrolled subjects. De-identified paraffin sections of pre- and post-study prostate tissue biopsy specimens will be deparaffinized by serial treatment with xylene, decreasing concentrations of ethanol followed by rehydration with distilled water. Sections will then be pretreated with 0.1% Triton-X100-TBS buffer for 5 min and incubated in 3% H_2O_2 -TBS buffer for 30 min at room temperature to eliminate endogenous peroxidase activity. Following 1hr blocking with 5.0% serum (horse or goat), the sections will be incubated overnight with primary antibodies. The next day, sections will be washed three times (5min/wash) with 0.1% Triton-X100/TBS buffer to remove excess primary antibody. Thereafter, primary antibodies will be detected using HRP-conjugated mouse or rat IgG VECTASTAIN ABC kit and DAB/substrate reagents (Burlingame, CA) according to the manufacturer's instructions. Assessment of the intensity of the immunohistochemical staining (from negative to 4+) will be performed by the

collaborating Pathologist, [name], who will be blinded to the randomization. It must be noted that only core biopsies containing tumor tissue (positive cores) can be informative, and that the paucity of tissue in each core biopsy may allow the testing of a limited number of biomarkers. It is also possible that all biopsy specimens from a particular subject will be needed for diagnostic purposes, and none will be available for research purposes. In any case, we will make every effort to measure the expression of as many relevant biomarkers as the availability of biopsy tissue specimens will allow.

Lab results, when feasible, will be reviewed by a member of the research team within 24 hours.

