Assessment of definitive treatment after repeat biopsy and final study visit will be performed by following subjects who return to their Urology clinic for standard of care visits. Serum levels of vitamin D_3 (cholecalciferol) will be determined by high-performance liquid chromatography (HPLC); 25(OH)D, $1,25(OH)_2D$, and parathyroid hormone (PTH) will be determined by radioimmunoassay (RIA), as previously described (38, 68). Serum levels of PSA will be measured in the VAMC Clinical Laboratories. Expression of VDR, p21, TGF β , COX-2, and NF κ B will be measured by immunohistochemistry on sections of pre- and post-study biopsy specimens of enrolled subjects. [name], Professor of Pathology and a Consultant for this study, will be responsible for determining the intensity of immunostaining on de-identified prostate biopsy sections from subjects enrolled in the study. Assessment of the intensity of the immunohistochemical staining (from negative to 4+) will be performed by the collaborating Pathologist, [name], who oversees Pathology Residents rotating through the Pathology Services of the Ralph H. Johnson VA Medical Center and MUSC and will be blinded to the supplementation status of the subjects enrolled in the study.

6. Statistical Considerations

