For aim 4, the expression of VDR, CYP27B1, p21, TGFβ, COX-2, and NFκB will be assessed by immunohistochemistry in pre- and post-treatment biopsy tissue specimens. As stated above, assessment of the intensity of the immunohistochemical staining (from negative to 4+) will be performed by the collaborating Pathologist, [name], who will be blinded to the randomization.

b) Sample Size Justification: The sample size was determined based on the ability to detect significant differences in the proportion of subjects with stable number of cores and stable pathology outcomes. Our assumptions regarding null and alternative hypothesis are based on our preliminary data from our single arm study of men receiving an intervention of vitamin D₃ alone with very similar inclusion/exclusion criteria. Our null hypothesis is that both arms will have 40% of men with stable number of cores, and our alternative is that the vitamin D₃ arm will have 70% of men with stable cores (and 40% in the placebo arm). Using a 2-sided alpha of 0.05, we have 87% power to detect this difference with 58 men per arm. Based on our preliminary data there are relatively few men who have an increase in Gleason without an increase in the number of positive cores, so we use the same sample size calculation to power the comparison of proportions of number of men with stable pathology. Examining trends in historical data and our previous study, we would expect 15% of men in the treatment arm to have additional treatment after repeat biopsy, compared to 40% in the placebo arm. This difference can be detected with 81% power - alpha of 0.05. From our earlier studies, we anticipate that some patients will drop out of the study, making them inevaluable for the primary endpoints which require end-of-study biopsy results. As such, we will enroll 68 patients per arm to ensure at least 58 evaluable patients per arm (i.e, allowing 15% dropout). This is a conservative estimate but consistent with previous experience. Aims 3 and 4 are secondary and, as such, power is not provided. Hypothesis testing across groups is not planned for these aims.

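### Aim 4 compares biopsies taken before and after the study, but the staining reader's stated masking covers only treatment arm

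*Combined protocol and SAP*

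**What the plan says.** - **The contrast.** Section A (Specific Aims), Aim 4: "To compare the expression of molecular biomarkers, which are prognostically relevant to prostate cancer progression, in pre- and post-treatment biopsy tissue specimens". The Analysis Plan (D.6 a) repeats this framing, with the markers "assessed by immunohistochemistry in pre- and post-treatment biopsy tissue specimens", and names no statistical method.
- **Use of the arms.** The Sample Size Justification (D.6 b) says of Aims 3 and 4: "Hypothesis testing across groups is not planned for these aims". It also calls both aims secondary and gives no power for them.
- **Masking.** The immunohistochemistry text in D.4 and the Aim 4 paragraph in D.6 a) describe the pathologist as one "who will be blinded to the randomization". D.5 says the same person "will be blinded to the supplementation status of the subjects enrolled in the study".
- **Slides.** D.4: "De-identified paraffin sections of pre- and post-study prostate tissue biopsy specimens will be deparaffinized". D.5 also has the reader grade de-identified sections. Neither says what the slide label shows.
- **Scale and tissue.** Intensity is a visual grade from negative to 4+. D.4 warns that "only core biopsies containing tumor tissue (positive cores) can be informative" and that tissue may run out. Section E.1.b lists the specimens as paraffin blocks from both biopsies.

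**The concern.** Masking should hide whatever factor is being compared. Hiding the arm suits Aim 1, where the arms are compared. In Aim 4 the two things compared are an early and a late specimen from the same man, and nothing stated hides which is which.

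Two mechanisms could then produce an apparent change without any biology. First, a reader who can tell that a slide is post-study may grade it in the expected direction. The background section on vitamin D and prostate cancer supplies such directions: p21 up, COX-2 down, NFκB signalling inhibited. Second, if early and late sections are stained on different occasions, differences between runs or antibody lots can coincide with time point.

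At stake is the interpretation of the biomarker results. A before/after shift in the vitamin D arm could be reported as a vitamin D effect when the placebo arm would have shown the same shift.

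**Working it through.** The plan gives no effect size, standard deviation or test for Aim 4, so there is no figure to reproduce. The check sets the sections side by side.

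1. **Factor compared (A, D.6 a).** Time point, within man. Arm does not appear in the wording of the aim.
2. **Factor masked (D.4, D.5, D.6 a).** Arm, in all three places. Time point is not mentioned in any of them.
3. **Does de-identification close the gap?** It removes the link to a person. A slide can carry a study code and still show a visit or date. Coding might hide the time point incidentally, but the text does not ensure it.
4. **Staining runs.** D.4 describes one procedure for both sets of sections but not when it is carried out. Paraffin blocks would allow a pair to be stained together; no section requires it.
5. **How far apart the tissue is collected.** D.4 times the repeat biopsy 12–18 months from the previous biopsy and/or enrolment. Section E.1.a allows a diagnostic biopsy up to 12 months before screening. Counted from enrolment, the gap could approach 12 + 18 = 30 months, plus up to 14 days for screening.
6. **What the placebo arm could do.** Let the true mean change be δ_D with vitamin D and δ_P with placebo, and let *b* be a reader or run shift common to both arms. The observed changes are δ_D + *b* and δ_P + *b*. Each arm alone carries *b*; the difference is (δ_D + *b*) − (δ_P + *b*) = δ_D − δ_P, which does not. Masking to arm makes a common *b* plausible for reader expectation, but the benefit is realised only if the arms are set side by side.

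**Illustration, not an estimate.** Suppose the true change is zero, *b* is a uniform shift and a two-sided 0.05 paired t-test is used. All of this is assumed, including the SD σ of paired differences. The chance of a false change is P(|T| > t₀.₉₇₅,ₙ₋₁), with T noncentral t on n − 1 degrees of freedom and noncentrality *b*√n/σ. For n = 58, *b* = 0.25 and σ = 1.0, the noncentrality is 0.25 × 7.616 = 1.90 and the probability is 46.5%. The ranges below are for σ from 1.25 down to 0.75 grades:

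| Pairs | *b* = 0.1 | *b* = 0.25 | *b* = 0.5 |
|---|---|---|---|
| 58 (evaluable target per arm, D.6 b) | 9.2–17.0% | 32.2–70.4% | 85.0–99.9% |
| 30 (assumed, limited tissue) | 7.1–10.9% | 18.5–42.3% | 56.3–94.2% |

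This shows only that a modest shift would matter if it existed. It is no evidence that one would.

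**The case against.** The strongest reply is that this is silence, not a defect. The slides are de-identified, a laboratory manual may well code them, and blocks from both biopsies may be stained together at the end. A reader who does not know the arm also cannot tell which post-study slides come from treated men, which dilutes any expectation of a drug effect. Planning no hypothesis test between arms does not rule out showing the arms descriptively. The sentence that excludes such tests is itself weak ground, because D.6 a) plans to compare slopes across groups for Aim 3, which the sentence also covers.

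Much of this stands, and it rules out several stronger readings that a reader might infer:

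- **That the reader is unmasked to time point.** The documents show only that such masking is not stated.
- **That staining drift will occur.** It arises only if pairs are stained separately, and the schedule is not given.
- **That the shift has the same sign in every man, so that more patients cannot dilute it.** A consistent sign is plausible for reader expectation, or if all early slides go in one run and all late slides in another. With several runs, the sign can vary and partly average out.
- **That the reader would expect VDR to rise.** The background section gives no such direction.
- **That the placebo arm cannot help.** It can, if change is displayed by arm.

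The reply does not remove the mismatch. The plan states a masking rule for this reader three times, and each time it concerns a factor other than the one Aim 4 compares.

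**Conclusion.** The concern holds in limited form. The stated masking does not cover the stated contrast in Aim 4, and neither time-point masking nor same-run staining of paired sections is described. An apparent biomarker change could therefore reflect reader expectation or, if pairs are stained separately, run or lot differences. How large that might be cannot be derived from the documents.

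A reader might also infer that the trial's main result is compromised. It is not: Aims 1 and 2 compare arms, for which masking to arm is the relevant protection. The consequence is confined to a secondary, unpowered aim that depends on leftover tissue, so this is a worthwhile improvement rather than a serious flaw. The conclusion rests on reading D.4, D.5 and D.6 as written; a laboratory procedure that already codes slides by time point and stains pairs together would largely settle it.

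**What to change.** In D.4, D.5 and the Aim 4 paragraph of D.6 a), state that:

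- every section carries a random code that hides both arm and time point, and sections are read in random order;
- each man's early and late sections are stained in the same run with the same antibody lot;
- codes are broken only after scores are locked;
- within-man change is reported side by side for the two arms, so that a shift common to both is not read as a vitamin D effect;
- the number of men per arm with scorable tumour at both biopsies is given, since men without it contribute no pair.

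This needs the same slides, reader and antibodies, and no extra patients or biopsies. If baseline staining was intended earlier, it would wait for the repeat biopsy. Same-run staining does not remove differences due to block age; the side-by-side display by arm helps to show those. The change is best made before any slide is read, because a reading made with time point visible cannot be corrected in the analysis and scarce tissue may not allow restaining.

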Abnormal lab results will be reported to the PI and to the Clinical Co-Investigator within 72 hours (allowance for final results and communication over weekends). Critical lab values will be reported to the Clinical Investigator(s) immediately. Subjects and their Primary Care Provider will be notified of any unusual lab results for follow-up as determined by the Clinical Co-Investigator. Laboratory testing will be repeated if necessary. If a subject's serum calcium exceeds 10.5 mg/dl, confirmed via a second test,

the patient will be removed from the study, his Primary Care Provider notified and a follow-up appointment scheduled.

The CRC, PI and Co-Investigators will update and maintain the Regulatory Documents: protocol and amendments, personnel CV's, licenses and training, IRB, VA R&D and FDA correspondence; review and document the safety and research laboratory results; document the study medication receipt, dispensing, return and subject compliance; and maintain subject confidentiality with an assigned de-

identified number for source documents and electronic data entry.

5. Measurement of Primary Outcome: Assessment of tissue biopsy specimens will be performed as part of the standard of care for each subject by the VAMC and MUSC Pathologist, (who will be blinded to the randomization), according to the criteria listed in Table 1.

TABLE 1: DEFINITION OF RESPONSE (R), STABLE DISEASE (SD) AND PROGRESSION (P) OF PATHOLOGY BASED ON CHANGE IN GLEASON SCORE AND NUMBER OF POSITIVE CORES (OUT OF 12) AT BASELINE AND REPEAT BIOPSY.

		GLEASON SCORE		
		LOWER	SAME	HIGHER
Number of Positive Cores	Lower	R	R	Р
	SAME	R	SD	Р
	HIGHER	Р	Р	Р

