a) Analysis Plan: The first aim of this proposal is to determine whether vitamin D₃ supplementation, compared to placebo, is more effective in maintaining stable or lowered number of positive cores and Gleason score, assessed by the pathologist as per standard of care. Baseline and end-of-study biopsy will be compared in each patient by calculating the change in number of positive cores and the change in Gleason score. These will be described using summary statistics of the ordinal changes and graphical displays. Each patient will also be categorized using three binary indicators: (1) stable Gleason (better or the same score as baseline) vs. worse Gleason (higher Gleason score); (2) stable number of cores (fewer or the same number of positive cores) vs. higher number of cores (more positive cores than at baseline; (3) stable pathology, as defined in Table 1. In each arm of the study and for each outcome, the proportions will be estimated with 95% confidence intervals. Arms will be compared using Fisher's exact test with a 1-sided alpha of 0.05. We will focus on stable number of cores and stable pathology as we expect that there will be less significant changes in Gleason scores. The second aim focuses on additional treatment after the end-of-study biopsy. We will estimate the proportion of men in each group who go on to hormone therapy, prostatectomy, or radiation therapy along with their 95% confidence intervals. We will also compare the proportions across groups using a Fisher's exact test with 2-sided alpha of 0.05.

For aim 3, serum levels of PSA and 25(OH)D will be measured at baseline and every 16 weeks until the end of the study; cholecalciferol, 1,25(OH)₂D, and PTH will be measured at baseline and at the end of the study. Graphical displays will be created to show the trends by patient over time in each group. Linear longitudinal modeling will be used to estimate trajectories over time in each group and to estimate changes from baseline to each relevant time point. Slopes will be estimated and tested for differences from zero in each group. We also plan to compare slopes across groups. Associations between changes in each of these levels with changes in Gleason, number of positive cores, and need for definitive surgery will be estimated using logistic regression models (with pathology outcomes defined above as the outcome measures).

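### The protocol hypothesises improvement at repeat biopsy, but every planned Aim 1 arm comparison pools better with unchanged, so none of them tests improvement

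*Combined protocol and SAP*

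**What the plan says.** **The hypothesis.** Specific Aim 1 (section A) asks whether vitamin D3 improves pathology status relative to placebo. Section A goes on to identify a responder by a fall in Gleason score or positive cores. The opening of section D hypothesises a decrease in cores and Gleason score. The Concluding Remarks anticipate significantly more improving men in the intervention arm.

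**The analysis.** Section D.6 a) restates Aim 1 as "maintaining stable or lowered number of positive cores and Gleason score". Each man is reduced to three binary indicators: Gleason better or same vs worse; "stable number of cores (fewer or the same number of positive cores) vs. higher number of cores"; and "stable pathology, as defined in Table 1". The arms are compared on these by Fisher's "exact test with a 1-sided alpha of 0.05". Of the changes in cores and Gleason score, the plan says: "These will be described using summary statistics of the ordinal changes and graphical displays".

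**The classification.** Table 1 (section D.5) is headed "DEFINITION OF RESPONSE (R), STABLE DISEASE (SD) AND PROGRESSION (P) OF PATHOLOGY". Section D.4 has every man classified as improving, stable or progressing after the repeat biopsy.

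**The sample size.** Section D.6 b) assumes 40% vs 70% with stable cores: "Using a 2-sided alpha of 0.05, we have 87% power to detect this difference with 58 men per arm". For stable pathology it adds: "so we use the same sample size calculation to power the comparison of proportions of number of men with stable pathology".

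**The concern.** Improvement is the hypothesis and the expected conclusion, yet no between-arm test isolates it. The first two indicators count an unchanged man as a success alongside an improved one. The third points to a table with three categories and does not say how they become two, but on any reading it is not a test of Response. Aim 3's models relate laboratory changes to pathology and do not compare Response between arms.

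At stake is what a positive Aim 1 result would license. It would support a claim that fewer men progress. It would not, by itself, support the claim that more men improve. The pilot (section C) did compare responders between groups, so the trial as planned omits a contrast that its own preliminary evidence used.

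**Working it through.** **Inputs.** 58 evaluable men per arm and stable rates of 40% vs 70% (section D.6 b). The pilot results are in section C, Safety and Efficacy. In the 44 supplemented men, 55% improved, 5 (11%) did not change and 34% progressed, which gives counts of 24, 5 and 15. In the 19 historical controls the counts are 4 (21%), 3 (16%) and 12 (63%).

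**Method.** Exact power of Fisher's test: sum Bin(x; 58, p1) × Bin(y; 58, p2) over all pairs (x, y) whose Fisher p-value is at most 0.05.

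**1. The plan's own figure.** For 70% vs 40% the power is 87.6% at 2-sided 0.05, so the stated 87% reproduces. At the Analysis Plan's 1-sided 0.05 it is 93.8%.

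**2. The pilot's own comparisons.** Improvement, 24/44 vs 4/19: Fisher 2-sided p = 0.026 (reported 0.025). Not progressing, (24 + 5)/44 = 29/44 = 66% vs (4 + 3)/19 = 7/19 = 37%: p = 0.051 (reported 0.05). The pilot therefore made both contrasts; the trial plans only the second kind.

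**3. The stable rate does not fix the Response rate.** Stable is Response plus stable disease (R + SD). Each row below adds to 40% vs 70%. The splits are illustrations, because the documents give no planning rate for Response.

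| Response, placebo vs vitamin D3 | SD, placebo vs vitamin D3 | Planned pooled test positive (2-sided / 1-sided) | Direct Response test positive (2-sided / 1-sided) |
|---|---|---|---|
| 21% vs 21% | 19% vs 49% | 87.6% / 93.8% | 3.0% / 3.2% |
| 20% vs 35% (stable men split evenly) | 20% vs 35% | 87.6% / 93.8% | 37.1% / 49.4% |

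The pooled test behaves identically in both rows, so its result cannot tell them apart.

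**4. What a Response comparison could detect with 58 per arm.**

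| Response, vitamin D3 vs placebo | Fisher power (2-sided / 1-sided) |
|---|---|
| 24/44 (55%) vs 4/19 (21%), pilot rates | 95.2% / 97.8% |
| 45% vs 21% | 74.0% / 82.9% |
| 35% vs 20% | 37.1% / 49.4% |

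From 21%, 80% power needs a difference of about 26 points (2-sided) or 23 points (1-sided). The 95% CI half-width is 1.96 × √[p1(1−p1)/58 + p2(1−p2)/58]. This gives 1.96 × √(0.55×0.45/58 + 0.21×0.79/58) = 16.5 points near the pilot rates and 14.8 points at 21% vs 21%.

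**5. Meaning of stable pathology.** In Table 1 the cells that are not P are the four in which neither Gleason score nor positive cores rise: three R and one SD. Those are the men who are stable on both of the first two indicators. Applied to the pilot, R or SD gives 66% vs 37%, close to the planned 70% vs 40%, with power 85.1% / 92.2%.

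**6. Randomisation strata.** Section D.4 (Visit 2) stratifies randomisation by baseline 25(OH)D; the Aim 1 test ignores the strata. The documents give neither cut-points nor any association with outcome. Assume two or three strata, a lowest-to-highest odds ratio of 1 to 5, and overall rates held at 40% and 70%. In simulation, a Cochran-Mantel-Haenszel (CMH) test then gains 0 to 0.4 point over an unstratified chi-square test at 1-sided 0.05, and 0 to 1.9 points at 2-sided 0.05. The 1-sided size of an uncorrected asymptotic test reaches 5.7% when the common rate is 50%; Fisher's is 3.6% at 40%.

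**The case against.** The strongest reply is that pooling is deliberate. The pilot's second objective was stabilisation or improvement, and its report compared progression between groups. Sections D.6 a) and b) agree with each other on the pooled outcome. The wording in Specific Aim 1 and in section D is relative to placebo and can be read as a better outcome for the group. Only the Concluding Remarks say outright that significantly more men will improve, and that is an expectation, not an analysis. Most of this stands: pooling is a reasonable outcome for the aim as the Analysis Plan restates it. It does not supply a test for the improvement claim, and section D's hypothesis of a decrease is hard to read as the absence of an increase.

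The equal-Response scenario is constructed, and the pilot runs against it: stable disease was 16% in controls and 11% in supplemented men, so the whole gain was in Response. That also stands. The scenario shows what a positive test cannot exclude, not what is likely.

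Four stronger readings are tempting and are not supported.
- A reader might infer that stable pathology is undefined and could mean SD alone, which in the pilot points the other way. The aim as restated, the meaning given to stable in the other two indicators, and the shared sample size calculation all imply R or SD vs P.
- A reader might infer a power error. There is none; 87% reproduces.
- A reader might infer that pooling is itself a mistake. It is not, for the aim as the Analysis Plan states it.
- A reader might infer that ignoring the strata invalidates Fisher's test or calls for CMH in its place. Fisher remains valid and somewhat conservative. An uncorrected 1-sided CMH test would exceed its nominal size for very little gain from the strata.

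**Conclusion.** The concern holds as a mismatch between claim and test. No planned between-arm comparison addresses improvement, so a positive Aim 1 result could not by itself support the statement in the Concluding Remarks. This follows from the definitions and does not depend on the illustrative rates. The planned test keeps its 87.6% (2-sided) or 93.8% (1-sided) chance of success whatever the split between Response and stable disease, including a split with no difference in Response.

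The power figures for a Response test rest on pilot rates from 44 and 19 men with historical controls. In addition, the pilot required fewer positive cores for improvement, while Table 1 also counts unchanged cores with a lower Gleason score as R. The pilot's 55% and 21% are therefore a slightly narrower quantity than R.

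Two further items belong here. The Aim 1 alpha differs between the Analysis Plan and the Sample Size Justification, which is a real inconsistency. The definition of stable pathology needs only a clarifying phrase.

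**What to change.** 1. Add one labelled secondary comparison of the proportion with Table 1 Response (R vs not R) between arms, with the difference and its 95% CI. Otherwise, reword Specific Aim 1, the section D hypothesis and the Concluding Remarks to absence of progression. An ordinal test across R, SD and P is no substitute: in simulation a 2-sided Wilcoxon test is positive 66.5% of the time in the equal-Response scenario above.
2. State one alpha and one sidedness for Aim 1 in both parts of section D.6.
3. Write out stable pathology as R or SD vs P.
4. Optionally, report beside the planned Fisher test an analysis stratified by baseline 25(OH)D (a stratified risk difference with CI, or an exact stratified test), with the number of strata and cut-points given. Keep Fisher as the main test.

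**Cost.** Analysis-plan wording and a few lines of code; no new data, visits or patients, because the three-way classification is already collected. The downside is one more secondary analysis to report. It is well powered only for differences near the pilot's, so its confidence interval, with a half-width of about 15 to 17 points, should carry the interpretation.

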Safety and Efficacy: Supplementation with vitamin D₃ at 4000 IU per day for one year appeared to correct all cases of vitamin D deficiency, although the magnitude of the response varied among subjects. No adverse events linked to vitamin D₃ supplementation at 4000 IU per day were observed. Serum PSA levels (expressed as median ± SD in ng/mL) remained relatively constant and changes do not appear to be related to the baseline PSA level (entry: 4.1±1.8 vs. exit: 4.5±2.7; p=0.27). Furthermore, serum PSA levels did not seem to correlate with the repeat biopsy outcome. To determine whether individual subjects improved or progressed, we compared the number of positive cores and Gleason grade at baseline and repeat biopsy. By these criteria, 34% of these subjects progressed; five subjects (11%) showed no change; however, more than half of the subjects (55%) showed improvement, defined as a decrease in positive cores and no increase in Gleason score at repeat biopsy. We also compared the number of positive cores and Gleason grade at baseline and repeat biopsy in the supplemented group and the control group. Using the same criteria, 63% of the subjects in the control group progressed (because of an increase in the number of positive cores or in Gleason score), compared to 34% in the supplementation group (p=0.05). Furthermore, in the historical control group, four patients (21%) had improvements in biopsy results, three showed no differences (16%), and twelve (63%) progressed. Comparing the proportions who responded in each group, a significant difference was found (p=0.025) (68).

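### Aim 1 is tested at one-sided 0.05, but the trial is sized at two-sided 0.05, so the written test doubles the nominal false-positive rate in favour of vitamin D (0.05 instead of 0.025)

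*Combined protocol and SAP*

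**What the plan says.** **Analysis (section D.6 a, Analysis Plan).** Each man is classified by three binary indicators: no rise in Gleason score, no rise in the number of positive cores, and stable pathology as defined in Table 1. The arms are compared on these by Fisher's "exact test with a 1-sided alpha of 0.05". The same paragraph tests Aim 2, additional treatment, by Fisher's "exact test with 2-sided alpha of 0.05".

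**Sample size (section D.6 b, Sample Size Justification).** The calculation concerns "the proportion of subjects with stable number of cores and stable pathology outcomes", the same Aim 1 outcomes. It takes 40% stable cores on placebo and 70% on vitamin D, and states: "Using a 2-sided alpha of 0.05, we have 87% power to detect this difference with 58 men per arm". The result is reused for stable pathology because "there are relatively few men who have an increase in Gleason without an increase in the number of positive cores".

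**Which indicator decides.** The analysis plan says: "We will focus on stable number of cores and stable pathology as we expect that there will be less significant changes in Gleason scores". Section D.5, headed "Measurement of Primary Outcome", points instead to the single Table 1 classification.

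**The concern.** The two parts of section D.6 give different tests for the same comparison, and neither gives a reason for the difference. If the analysis plan is followed, a result in favour of vitamin D with a two-sided p-value between 0.05 and about 0.10 counts as a success. By the criterion the trial was sized for, the same result is a failure. The choice could be made after the data are seen, and the conclusion on the trial's first aim could turn on it. Aim 2 is two-sided, so one-sided testing is not a general policy of the plan.

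The lack of a single named deciding indicator is a related, smaller matter. It leaves a second choice open at the analysis.

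**Working it through.** **Inputs.** All are from section D.6: 58 evaluable men per arm; 40% stable in both arms under the null; 70% versus 40% under the alternative; Fisher's exact test; alpha 0.05, one-sided in a) and two-sided in b).

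**Step 1: reproduce the stated 87%.** Continuity-corrected normal approximation, with p̄ = (0.70 + 0.40)/2 = 0.55:

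z = [0.30 − 1/58 − z_α √(2 × 0.55 × 0.45/58)] / √[(0.70 × 0.30 + 0.40 × 0.60)/58]

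- The roots are √0.008534 = 0.0924 and √0.007759 = 0.0881, and 1/58 = 0.0172.
- Two-sided 0.05 (z_α = 1.960): z = (0.3000 − 0.0172 − 0.1811)/0.0881 = 1.154, power 87.6%.
- One-sided 0.05 (z_α = 1.645): z = (0.3000 − 0.0172 − 0.1520)/0.0881 = 1.485, power 93.1%.

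Exact power was found by applying Fisher's test to all 59 × 59 = 3,481 possible pairs of counts and summing the binomial probabilities of those that reject.

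| Test | Exact power, 70% vs 40% | Continuity-corrected power | n per arm for 87% (continuity-corrected) |
|---|---|---|---|
| Two-sided 0.05 | 87.6% | 87.6% | 58 |
| One-sided 0.05 | 93.8% | 93.1% | 48 |

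The stated 87% and 58 per arm are a genuine two-sided calculation, not a one-sided figure with the wrong label. Without the continuity correction, two-sided power would be 91.2%, which also does not match.

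**Step 2: error rate in favour of vitamin D.** The nominal rate is 0.05 under a) and 0.05/2 = 0.025 under b). Exact rates from the same enumeration:

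| Common stable rate | One-sided 0.05 | Two-sided 0.05, favourable side |
|---|---|---|
| 40% | 3.6% | 1.5% |
| 50% | 3.9% | 1.6% |

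At 40% the unrounded values are 0.0358 and 0.0153, a ratio of about 2.3. One-sided 0.025 and two-sided 0.05 reject in favour of vitamin D on exactly the same tables (0 of 3,481 differ).

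**Step 3: which results change verdict.** Take 23/58 (40%) stable on placebo.

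| Vitamin D stable | One-sided p | Two-sided p | Success under a) | Success under b) |
|---|---|---|---|---|
| 33/58 | 0.047 | 0.094 | yes | no |
| 34/58 | 0.031 | 0.063 | yes | no |
| 35/58 | 0.020 | 0.041 | yes | yes |

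The bar is 33 − 23 = 10 men (10/58 = 17 points) under a), and 35 − 23 = 12 men (12/58 = 21 points) under b).

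**Step 4: how often the rules disagree.** The probability that only the one-sided rule succeeds is 2.1% at 40% versus 40%, and 6.2% at the design's 70% versus 40%. At an assumed 57% versus 40% it is 14.9%. The 57% is not in the plan. It was chosen close to the one-sided bar of 33/58, so this is near the worst case.

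**Step 5: several indicators (secondary).** The documents give no joint rates, so these simulations (400,000 per scenario) rest on assumptions: stable cores in 40–50% of men, a Gleason rise in 2–5% of men with stable cores, and a Gleason rise in 5–30% of the others. The table shows the chance of at least one false claim for vitamin D.

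| Claim allowed on | One-sided 0.05 | Two-sided 0.05 |
|---|---|---|
| Either of the two focus indicators | 4.0–4.9% | 1.8–2.1% |
| Any of the three | 4.9–7.4% | 2.0–3.3% |

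Sidedness moves these rates more than the choice between two and three indicators does.

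**The case against.** The strongest reply is that Aim 1 is directional, so a one-sided test is legitimate, and that no passage sets a limit of 0.025. Both sections use a total alpha of 0.05. Fisher's test is conservative, so the actual one-sided error for a single indicator peaks at about 3.9% and does not reach 5%. The written test has more power than stated, not less. Only two vitamin D counts separate the rules when 23/58 are stable on placebo, and disagreement at the design rates is 6.2%.

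These facts are right, and they limit the point. The 0.025 is inferred from the two-sided sizing, and the doubling refers to the nominal rate in one direction. They do not remove the contradiction: one comparison has two success thresholds, with no statement of which governs and no reason given for the one-sided choice.

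The objection is stronger against the secondary point. The two focus indicators together stay below 5% even at the one-sided level, the plan itself plays down the Gleason indicator, and the joint rates are assumed. Section D.6 b) also refers to primary endpoints in the plural. Naming one primary indicator is therefore advisable, but the main finding does not depend on it.

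**Conclusion.** The concern holds. The Aim 1 test as written does not match the test for which the sample size and power were calculated, and it is the looser of the two. Its nominal error rate in favour of vitamin D is 0.05 rather than 0.025. On one indicator at a 40% common rate, the exact rates are 3.6% and 1.5%. The success bar is about 17 points rather than 21.

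These figures rest only on the plan's own rates, its 58 evaluable men per arm and Fisher's test. The 14.9% disagreement and the multiple-indicator ranges rest on the further assumptions stated with them. The trial is adequately powered under either rule. This must be corrected because it sets the decision threshold for the first aim.

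**What to change.** In section D.6 a), state the Aim 1 comparison as Fisher's exact test at two-sided alpha 0.05, or equivalently one-sided 0.025. Section D.6 b), the 58 evaluable and 68 enrolled per arm, and the 87% power for stable cores then stand unchanged. The cost is a few words and no patients. Power at 70% versus 40% goes from 93.8% to 87.6%, which is what the plan already claims. If the sponsor does intend one-sided 0.05, the other way to remove the contradiction is to justify it and rewrite section D.6 b) to match. That choice must be made before unblinding.

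Secondary: before unblinding, name one indicator as primary and treat the others as secondary. Table 1 stable pathology would agree with section D.5; stable cores would agree with the rates used for sizing. If stable pathology is chosen, give its power from its own rates. In the pilot, "63% of the subjects in the control group progressed" against 34% of supplemented men, so 100 − 63 = 37% and 100 − 34 = 66% did not progress. Those rates give 84.9% two-sided power with 58 per arm, although they come from only 44 treated men and 19 historical controls.
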